7.6.2.6 Vital Signs

Values and changes from baseline for vital sign measurements will be summarized by treatment group at each scheduled time point using descriptive statistics.

7.6.2.7 Physical Examination Findings

All physical examination abnormal findings will be listed per subject.

7.6.2.8 Daily Urinary Output

Cumulative urinary output is collected daily at Hour 24, 48, 72, 96 and 120. Daily urinary output will be summarized descriptively for all treated subjects by treatment for each time point.

7.6.2.9 Oxygen Saturation

Oxygen Saturation will be summarized descriptively for all treated subjects by treatment for each time point as well as change from baseline.

7.7.1 7-Point Likert Scale

Both the percentage of subjects reporting moderate or markedly improved resting dyspnea and percentage of subjects reporting moderate or marked improvement using the patient global assessment on a 7-point Likert scale will be analyzed and presented in the same manner as the primary endpoint at Hours 6, 12, and 24. Missing values for the Likert scale at Hours 6, 12, and 24 will only be imputed, if a score cannot be obtained because the subject has died or is physically unable to complete the form. In these cases, a worst score imputation (i.e. -3) will be used for that time point.

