5.7 Outcomes Research Assessments

5.7.1 Dyspnea Assessments

The sensation of dyspnea is subjective, but dyspnea relief is important to subjects and has been long quantified in clinical trials using patient-reported outcome scales that have previously been used to assess the efficacy of other interventions in ADHF subjects.

In this trial, subjects are asked to report their absolute current severity of dyspnea on an 11-point numerical rating scale (NRS; range 0 to 10) and their current level of dyspnea relative to baseline using 7-level Likert scales.

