5.7.1.2 Dyspnea Likert Scale

Subject will be presented with the following question: “We would like to measure how you think your breathing is. Please circle the number next to the description that best indicates how you are breathing right now, compared to when you first started the study drug.”

3 = Markedly better

2 = Moderately better

1 = Minimally better

0 = No change

-1 = Minimally worse

-2 = Moderately worse

-3 = Markedly worse

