8 STATISTICAL CONSIDERATIONS

8.1 Sample Size Determination

For Part I (Cohort 1), approximately 50 subjects per group will be randomized to placebo or an incremental dose of BMS-986231 (3 - 6 - 12 µg/kg/min). Under a sample decision rule (eg, observed doubling with more than a 4% difference) and assuming clinically relevant hypotension incidences of 5% or 10% in the placebo group, the posterior probabilities of detecting an increase of 4-fold or 3-fold in incidence, respectively, are 86% and 80%, respectively. If there is no increase in clinically relevant hypotension, then the posterior probabilities of falsely detecting an increase are 11-12%.

For Part II (Cohort 2), approximately 70 subjects per group will be randomized to placebo or one of the two active dose levels of BMS-986231. Under a sample decision rule (eg, observed 1.8-fold increase with more than a 3% difference) and assuming clinically relevant hypotension incidences of 5% or 10% in the placebo group, the posterior probabilities of detecting an increase of 3-fold or 2.5-fold in incidence, respectively, are 82% and 80%, respectively. If there is no increase in clinically relevant hypotension, then the posterior probabilities of falsely detecting an increase are 13-15%. These probabilities do not reflect multiple comparison.

While the enrollment in the main study protocol will continue until 210 patients have been randomized globally in Part II (Cohort 2), enrollment may continue further only in Japan until approximately 18 total Japanese subjects are randomized

With regards to overall performance for selection of a maximally tolerated dose, a sample size of 50 per group for Part I (Cohort 1), along with 70 per group for Part II (Cohort 2) will identify a maximally tolerated dose approximately 50-70%, based on detecting an increase of 3-fold or 2.5-fold in incidence, and using sample decision rules that are consistent with above. Also, the design will provide an option to select a titrated 12 µg/kg/min dose approximately 60% of the time when that dose is tolerated, but a non-titrated 12 µg/kg/min dose is not tolerated. Conversely, the study design will not identify a maximally tolerated dose from Part II (Cohort 2) approximately 80%-85% of the time when no maximally tolerated dose exists

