7.1 General Methods

Results from Part I (Cohort 1) and Part II (Cohort 2) will be presented separately, unless otherwise noted.

Except as noted otherwise, descriptive summaries will be presented for continuous variables using number of subjects (N), mean, standard deviation (SD), median, minimum and maximum. Descriptive summaries for categorical variables will utilize counts and percentages. Several analyses noted in subsequent sections will present 95% confidence intervals (CIs), but no pre-specified significance testing will be included.

Adverse events and medical history will be coded according to the most recent Medical Dictionary for Regulatory Activities (MedDRA) version. Previous and concomitant medications will be coded using the WHO Drug Dictionary.

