7.6.1 Primary Safety Analysis

The incidence of clinically relevant hypotension from the start to 6 hours after the end of study drug infusion will be summarized by treatment. Point estimates and 95% confidence interval (CIs) for event rates will be presented by treatment, together with point estimates and 95% CIs for the risk difference and relative risk between each BMS-986231 arm and placebo. The confidence intervals will be calculated using an exact method. The 95% confidence intervals for the relative risk and risk difference will be obtained using an exact procedure that inverted the 2-sided test statistics (Agresti and Min, 2001)¹.

The event rate is calculated as the number of subjects experiencing at least one clinically relevant hypotension from the start to 6 hours after the end of study drug infusion, divided by the total number of subjects receiving study treatment.

The incidence of symptomatic hypotension up to 6 hours after the end of study drug infusion, as well as the incidence of SBP < 90 mm Hg (confirmed by a repeated measure) will be analyzed and presented in the same manner as the primary endpoint.

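### SAP 7.7.1 reports the two 7-point Likert scales only as a responder percentage; a seven-level table and one ordinal estimate beside it would use the rest of the answers

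*SAP*

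**What the plan says.** Protocol 5.7.1 has patients report "their current level of dyspnea relative to baseline using 7-level Likert scales". The answers to the dyspnea question in Protocol 5.7.1.2 run from +3 (markedly better) through 0 to -3 (markedly worse). The patient global assessment is also a 7-point Likert scale.

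SAP 7.7.1 turns each scale into a responder rate. It names "Both the percentage of subjects reporting moderate or markedly improved resting dyspnea" for the first, and for the second says that the "percentage of subjects reporting moderate or marked improvement using the patient global assessment on a 7-point Likert scale will be analyzed and presented". Three times are analysed, Hours 6, 12 and 24, and the approach is borrowed from the primary endpoint. A score that is missing because the patient died or could not complete the form is set to -3.

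The method carried over is that of SAP 7.6.1: event rates, risk differences and relative risks with exact intervals. "The 95% confidence intervals for the relative risk and risk difference will be obtained using an exact procedure that inverted the 2-sided test statistics".

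SAP 7.1 sets the inferential frame: "Several analyses noted in subsequent sections will present 95% confidence intervals (CIs), but no pre-specified significance testing will be included".

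The visible text has no ordinal summary of these scales and no seven-level table.

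**The concern.** The cut puts a patient who is minimally better in the same group as one who is markedly worse. Any difference between arms within the lower five levels is lost. The worst-score rule loses most of its force too: under the cut, -3 for a patient who has died counts exactly as +1 does.

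Other graded items in the same SAP keep their levels. The 0 to 10 dyspnea NRS is modelled on its full scale (7.5.2), and signs of congestion and the sensory and motor items get shift tables by category (7.7.3, 7.7.4). The visible text gives no reason for treating the Likert items differently.

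At stake is how precise, and how complete, the supportive patient-reported evidence is. With 50 or 70 per arm and a 95% interval as the only inferential output, interval width matters. The trial's main conclusion, on hypotension, is not affected.

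**Working it through.** **The plan's own figures.** None concerns the Likert scales. The only operating characteristics are those for hypotension in Protocol 8.1. Exact binomial enumeration of the Part II rule gives 81.7% and 79.7% (stated 82% and 80%). The Part I rule gives 85.9% and 80.3% (stated 86% and 80%). These agree but say nothing about the present point.

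**Inputs from the documents.** Protocol 8.1 gives 50 per arm in Part I; for Part II, "For Part II (Cohort 2), approximately 70 subjects per group will be randomized". The scale has seven levels, and the cut is at +2 or above.

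**Assumed inputs.** The documents give no Likert distribution or effect size, so the following are assumptions:
- placebo distributions, best to worst level, of (5, 15, 35, 33, 7, 3, 2)%, (12, 23, 32, 23, 6, 2, 2)% and (25, 30, 25, 13, 4, 2, 1)%, that is, responders of 20%, 35% and 55%;
- a common odds ratio of 1.8, 2.2 or 2.6 across all levels;
- a two-sided 5% level, used only to translate precision into power.

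**Precision.** Let p̄ be the level probabilities averaged over the two arms and r̄ the averaged responder rate. The information in the ordinal analysis relative to the cut is

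[(1 − Σp̄³)/3] / [r̄(1 − r̄)].

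Worked example, placebo 35% and odds ratio 2.2:
- the active responder rate is 54.2%, so r̄ = (0.350 + 0.542)/2 = 0.446;
- Σp̄³ = 0.0577;
- the ratio is (0.9423/3)/(0.446 × 0.554) = 0.314/0.247 = 1.27;
- the interval on the log odds ratio scale is wider by √1.27 = 1.13, or 13%.

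Over the nine combinations of distribution and odds ratio the ratio runs from 1.26 to 1.62. Since √1.26 = 1.12 and √1.62 = 1.27, the interval is 12% to 27% wider. Put differently, the ordinal analysis is worth 1.26 to 1.62 times as many patients.

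**The same loss as power.** Simulated power at odds ratio 2.2, score test on the cut against the tie-corrected Wilcoxon test, 5,000 trials per setting:

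| Placebo responders | 70 per arm: cut / ordinal | 50 per arm: cut / ordinal |
|---|---|---|
| 20% | 55% / 73% | 43% / 58% |
| 35% | 64% / 73% | 51% / 58% |
| 55% | 59% / 72% | 46% / 57% |

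Over all 18 settings the gap is roughly 6 to 18 points. A repeat with 40,000 trials per setting agreed with the table within 2 points and gave gaps of 5.4 to 18.2.

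**A nearby set of assumptions.** With responders of 20% to 60%, odds ratios of 1.5 to 2.5 and 70 per arm, the gap is 4 to 17 points against the ordinary binary test. It is 4 to 20 points against an exact binary method closer to the SAP's.

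**When the sign reverses.** Keep the same three placebo distributions at 70 per arm, but let the drug only move 15 percentage points of patients from minimally to moderately better. Power is then about 52%, 44% and 44% for the cut, against 13%, 14% and 14% for the Wilcoxon test.

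**The case against.** The strongest case for leaving the section alone has five parts.

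- **Power is not planned for.** With no significance test, a reader who infers that the trial forfeits a fixed 6 to 18 points of power goes beyond the documents. This stands: the loss is one of precision, and its size rests entirely on assumed distributions.
- **The loss is not certain.** The proportional shift is the setting in which an ordinal analysis is expected to win. If the effect lies at the cut, the responder percentage is much the more sensitive, and a win probability has the same weakness as the Wilcoxon test. This stands, and it is why the percentage should not be demoted.
- **The scales rank low.** They are neither primary nor secondary. A reader might infer that they drive the interim decisions, but Protocol 8.5 and SAP 7.11 list infusion completion, interruptions, hypotension and renal function, and name no Likert scale. This stands.
- **Dyspnea already has a full-scale analysis through the NRS.** This stands in part. SAP 7.5.2 models the NRS at Hours 24, 48 and 72, although the endpoint in SAP 4.1.2 also lists Hours 6 and 12. As written, the Likert percentages are the only visible patient-reported comparison between arms at those two early times. The patient global assessment has no full-scale counterpart at all.
- **Text is redacted.** The exploratory-endpoint material is blacked out or missing, and table layouts are left to a Data Presentation Plan that is not included. An ordinal analysis, or a reason for the cut, may be there. This stands as a limit on the claim.

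A responder percentage with a risk difference is also easy to interpret and matches the SAP's other binary outcomes. That argues for keeping it, not for reporting nothing else.

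**Conclusion.** The point holds as a cheap improvement to a supportive analysis. In the visible SAP both scales are reported only above or below the cut, so movement in the lower five levels and the meaning of the -3 score are lost.

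Under a proportional shift with odds ratio 1.8 to 2.6 and placebo responders of 20% to 55%, all assumed, the log odds ratio interval is about 12% to 27% wider than it need be. That is equivalent to roughly 6 to 18 points of power at 50 or 70 per arm. Under an effect confined to the boundary between minimally and moderately better, the planned percentage does better.

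The documents do not support two stronger conclusions: that the responder percentage is wrong and should be replaced, or that the trial's main findings or dose decisions are weakened by it.

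**What to change.** In SAP 7.7.1, keep the responder percentage with its exact 95% interval at Hours 6, 12 and 24. For each item and time point add:

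- a table of all seven levels by arm;
- one prespecified ordinal estimate with a 95% interval for each BMS-986231 arm against placebo. This would be either a common odds ratio from a proportional-odds model adjusted for region (the randomisation stratum in SAP 2.2) or a win probability stratified by region.

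Keep -3 for death or inability. Choose the estimate before unblinding. If redacted text already specifies an ordinal analysis, a cross-reference in 7.7.1 is enough.

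Cost: one standard model per item and time point and no new data. The proportional-odds model brings its own assumption, which the seven-level table lets readers judge. Either ordinal estimate is less sensitive than the cut if the effect lies only between minimally and moderately better, which is the reason to report both.

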7.7.2 Worsening Heart Failure and Worsening Renal Function

The Investigator will be asked to indicate if a subject has experienced worsening heart failure, to document the signs, and symptoms that led to the assessment of worsening heart failure, and to document the intensification of treatment implemented for worsening heart failure. Assessment is to be done once daily covering the prior 24-hour period as per the scheduled times. Worsening heart failure is defined as new or worsening signs and/or symptoms of heart failure that require:

- Intensification of IV therapy for heart failure (such as initiation, restart, or up-titration of IV diuretics, IV nitrates or other IV vasoactive drugs), and/or
- Addition of a mechanical support, either:
 - Ventilatory (mechanical ventilation, noninvasive ventilation),
 - Circulatory (Intra-Aortic Balloon Pump (IABP), ventricular assist device) or
 - Use of ultrafiltration, hemofiltration or hemodialysis specifically for the management of WHF

Supportive evidences (new or worsening signs or symptoms, intensification of IV heart failure medications, and/or addition of mechanical support) for worsening heart failure collected in CRF page will be tabulated. Signs and symptoms of worsening heart failure and IV heart failure medications for subjects experiencing worsening heart failure will be listed.

The percentage of subjects reporting with an episode of worsening heart failure and percentage of subjects reporting worsening renal function will be analyzed and presented in the same manner as the primary endpoint.

7.7.3 Congestive Heart Failure

Shift analysis will be performed for changes in physical signs of congestive heart failure through Hour 120 to evaluate qualitative changes that occurred through Hour 120. A shift table will be generated for each physical sign to tabulate per-subject changes between the categories at baseline and at each study time point.

7.7.4 Sensory and Motor Function

Shift analysis will be performed for changes from baseline in items related to patient assessed peripheral sensory and motor function. A shift table will be generated for each item to tabulate per-subject changes between the scores at baseline and at each study time point.

7.8 Pharmacokinetics

Blood samples will be collected from all subjects at 0.75, 4, 8, 14, and 48 hours during infusion and 4 hours after end of infusion and plasma concentrations will be measured using LC-MS. In addition, a PK sample will be collected from the subject when the dose is lowered due to a safety event and also at time of early discontinuation of study drug. Pharmacokinetic parameters for BMS-986231 and BMT-284730 and other metabolites (e.g., BMT-279554 and CAR-000463) will be estimated as appropriate. The plasma concentration data will also be used to conduct population pharmacokinetic analysis and exposure-response analysis with select efficacy and safety endpoints. Results of the population pharmacokinetic and exposure-response analysis will be reported in a separate report.

The PK population will be used for all listings. Evaluable PK population will be used for summaries and statistical analyses. Geometric mean and coefficient of variation (%CV) will also be presented for sample plasma concentration-time data. Analysis will include all analyte data in the PK dataset for BMS-986231 and metabolites of BMS-986231.

Subject plasma concentration-time profiles will be listed and summarized by treatment and nominal collection time for each analyte. Plots of mean (+SD) plasma concentration profiles versus time will be presented for each analyte, and all treatments will be superimposed on the same plot. Concentration at the end of infusion will also be summarized by treatment, which is the concentration at hour 48 for subjects completing 48 hours infusion and the concentration collected at early discontinuation for subjects not completing 48 hours infusion. The PK samples collected when the dose is lowered due to a safety event will be listed.

7.10 Outcomes Research

For the index hospitalization, length of stay from start of infusion to discharge and length of stay in the ICU/CCU will be summarized descriptively (see [section 7.1](#), including the first and third quartiles) for all treated subjects by treatment.

Following discharge from the index hospitalization, the percentage of subjects with rehospitalizations and emergency department visits will be summarized descriptively by treatment group for heart failure or other cardiovascular disease separately through Day 32 and will be analyzed and presented in the same manner as the primary endpoint.

Rehospitalizations will include subjects who are either under observation or admitted as an inpatient with a length of stay ≥ 24 hours. Emergency department visits will include urgent, unplanned visits in a monitored healthcare setting with a length of stay < 24 hours. Only emergency department visits that do not result in a hospitalization will be counted as separate healthcare encounters. Number of days alive and out of the hospital will also be summarized for all treated subjects by treatment.

7.11 Interim Analyses

Two interim analyses will be performed for this study. An interim analysis will be performed following the completion of the last visit at Hour 120 in Part I (Cohort 1). The analysis will include data for all Cohort 1 subjects through at least Hour 120. The DMC, Executive Committee and representatives from the Sponsor will assess hypotension, as well as additional safety information, in addition to any available endpoint events. The outcome will determine whether 12 $\mu\text{g}/\text{kg}/\text{min}$ is a sufficiently tolerated dose to be used in Part II (Cohort 2). The dose selection decision for Part II will be made by the Sponsor in collaboration with the Executive Committee, with input from the DMC.

The doses for Part II (Cohort 2) will be determined based on general guiding principles and considered in the context of the totality of the data. For example, some of the critical information that will be considered evaluating the suitability 12 $\mu\text{g}/\text{kg}/\text{min}$ for Part II will include the percentage of subjects completing the 48 hour infusion, percentage of subjects with temporary interruptions or permanent discontinuation of study drug, percentage of subjects with clinically relevant hypotension, percentage of subjects with symptomatic hypotension, and other key safety endpoints of interest (e.g. renal function).

The second interim analysis will be performed following completion of the last visit at Day 32 in Part II (Cohort 2) in order to facilitate drug development decisions. The study analysis team will

then provide top-line results to the project team. In addition to the two interim analyses, safety reviews after 20 patients in Part I (Cohort 1) and after 50 patients in each part will be performed.

No adjustments to confidence limits will be made as a result of interim analyses.

8 CONVENTIONS

8.1 Safety Data Conventions

Except as noted in [Section 7.6](#), safety data will be handled according to the BMS safety data conventions. This document includes descriptions on how to analyze AE data as well as how to handle partial dates, missing dates, and unknown end dates when analyzing safety data. If onset time of AEs is missing or incomplete, the onset date of AEs will be used to determine if the AEs will be included in the AE summary tables as follows.

- Non-serious AEs will be included in summary tables if the onset date is on or after the start date of study treatment and not later than the date of Hour 120.
- Serious AEs will be included in summary tables if the onset date is on or after the start date of study treatment and not later than the date of Day 32.

Clinically relevant hypotension defined in the primary endpoint consists of two components which are further clarified as follow:

- The component of “SBP < 90 mm Hg (confirmed by a repeated value < 90 mm Hg)” will be identified by a SBP measurement < 90 mm Hg with confirmatory SBP measurement < 90 mm Hg within 30 minutes after the initial qualifying value. If a confirmatory SBP is missing, the initial SBP will be treated as confirmed if no SBP measurement \geq 90 mm Hg within 30 minutes exists. The assessment time of the initial SBP < 90 mm Hg will include time from start of infusion, up to and including 6 hours after end of infusion.

The confirmatory measurement should be within 15 minutes; however, a window of up to 30 minutes will be applied, to determine if a qualifying confirmatory value is obtained.

- The component of “symptoms of hypotension” will be identified by at least one symptom (other than “low blood pressure”) from the CRF page collecting signs and symptoms of low blood pressure with onset time from start of infusion, up to and including 6 hours after end of infusion

This clarification is also applied to the safety endpoints “The incidence of symptomatic hypotension up to 6 hours after the end of study drug infusion, as well as the incidence of SBP < 90 mm Hg (confirmed by a repeated value)”.

Subjects counted in the endpoint “Percentage of subjects with discontinuation due to symptomatic hypotension” are those who have “Hypotension” as the reason for discontinuation and have a symptom (other than “low blood pressure”) from the CRF page collecting signs and symptoms of low blood pressure with onset time on or before the time of dose discontinuation.

Subjects counted in the endpoint “Percentage of subjects with down-titrations, interruptions or discontinuations as a result of low blood pressure, either protocol specified clinically relevant hypotension, or asymptomatic decreases” are those who have ‘Hypotension’ as the reason for rate reduction, infusion interruption or discontinuation.

